### **Description of Control Group**

Participants enrolled in control sites will receive four assessment contacts on the same schedule and in the same manner as the participants enrolled in intervention sites. Their assessments will include the TTM constructs of Stages of Change, DB, and V/B, using the same scales as administered to participants in the intervention group. However, they will not receive any feedback. The purpose of this assessment is to control for historical trends and the potential reactivity of assessment alone. Apart from these assessments, participants enrolled in control sites will receive usual care. In order to minimize the effect of asking about ACP behaviors on participants' engagement in these behaviors, the assessments will be masked. This will be accomplished by assessing participants' Stages of Change for several other behaviors that are relevant to the health of older persons, including a healthy diet, physical activity, and fall prevention.

### **Outcome Measures**

The primary and secondary outcomes will be based on the participant's stage of behavior change for each of the four ACP behaviors targeted by the intervention materials (see **C.1.c.**) obtained at six months following the baseline assessment. The primary outcome will be the proportion of participants achieving the stage of action or maintenance for all four ACP behaviors. The secondary outcomes include the proportion of participants achieving each stage for each of the four ACP behaviors.

These outcomes will be obtained through participant self-report by an interviewer who is blinded to the participant's group assignment. Although there is a potential concern that social desirability bias could result in differential reporting by participants in the intervention and control groups, there are several reasons why self-report is the best way to ascertain outcomes. First, there is no gold-standard objective measure for these outcomes. There are no incentives for physicians to document communication with patients regarding values and goals, so that underreporting of this communication in the medical record is likely to be substantial. Physician and/or surrogate self-report of communication is subject to the same social desirability bias, especially for physicians in the practices randomized to the intervention. It would be possible to ask participants for copies of ADs, but, if the intervention is successful in increasing communication, these may be given to surrogates and not be immediately accessible. Second, the intervention minimizes the likelihood of social desirability bias. Because the feedback reports and brochures acknowledge the difficulties

associated with behavior change, they provide participants with the message of engaging in behaviors when they are ready to do so, rather than with a message of needing to accomplish a certain behavior. In addition to these outcomes, responses to the scales used for the assessment will be examined as secondary outcomes.

### **Independent Variables**

The independent variables will be used to describe the study population and test for the adequacy of randomization. They will also be used as covariates in the models testing the study hypotheses. The independent variables will measure the constructs of sociodemographic status, health status, and psychosocial status. Sociodemographic variables include: age, gender, ethnicity, level of education, and income. Health status variables include: chronic conditions; functional status, measured using the instrumental activities of daily living scale, self-rated health, and self-rated quality of life. Psychosocial status variables include: religion and religiosity, measured using the Duke University Religion Index; instrumental and emotional support, measured using the EPESE social support items; and depression, using the PHQ-2. Participants will also be asked items taken from an earlier study on familial experiences with end-of-life decision making, as this has been demonstrated to be associated with readiness to engage in ACP. The independent variables will be obtained by self-report in the baseline assessment.

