### **Power and Sample Size**

Based on our cross-sectional data demonstrating a prevalence of between 4 and 8% for the primary outcome, we conservatively estimate that the prevalence of this outcome in the control group, which, because of our exclusion criteria, will be 0% at baseline, will be 5% at the Month 6 assessment. The sample size is based on the ability to detect an absolute increase of 10% for ACP for the treatment group over the control group at Month 6, consistent with effect sizes in previous TTM-tailored interventions and a judgment regarding a minimum clinically significant effect size. Sample size calculations assumed one-tailed significance testing at alpha = .05 and were based on a one-way analysis of variance for proportions with arcsine transformation and nested random effects for sites to accommodate the cluster-randomized design. Based on an enrollment of 16 sites for the study (8 matched pairs), to achieve power of .80 for the primary outcome, a final sample size of 50 individuals per site is needed, resulting in a final study sample size of 800. Assuming 20% loss to follow-up, a baseline sample size of 1000 is required.

This sample size will also be sufficient for conducting process-to-outcome analyses assessing the effects of potential mediators and moderators of outcomes using multiple regression or structural equation modeling analyses. For example, for structural models of reasonable size (e.g., df = 40–50), and assuming a close fit criterion (RMSEA = .05), power is at least .80 for groups of about 240.

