### **Analysis**

The analysis is based on the study design of two groups (intervention, control) X four occasions (baseline, 2, 4, 6 months) with sites nested in groups based on cluster randomization of matched pairs of sites. Baseline analyses will include examination of group differences to evaluate the success of the matched-pairs randomization procedure and examination of potential covariates to reduce the expected within-groups dependency resulting from cluster randomization.

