### **Primary Outcome**

The main outcome hypothesis is that the proportion in Action/Maintenance for the four ACP behaviors is intervention group > control group at the final 6-month assessment. Several analytical approaches are available within a more general framework of random effects

modeling incorporating both time and site level effects in addition to potentially important covariates. The basic analytical approach will employ the generalized estimating equation (GEE) method to analyze intervention main effects and interaction (additive) effects. GEE enables use of linear, logistic and Poisson regression methods with repeated measures, providing consistent estimates of regression coefficients and robust variance estimates, even in the presence of unbalanced group data. It permits the clustering of sites by treatment condition and provides a direct estimate of the ICC.

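### With 16 sites, the primary GEE test has no stated small-sample correction and an open list of 13 to 15 covariates, so a one-sided 5% test could run at about 7 to 11%

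*Combined protocol and SAP*

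**What the plan says.** **Independent Variables** names three groups of baseline measures. Five items form the first group: "Sociodemographic variables include: age, gender, ethnicity, level of education, and income". Four more concern health, and that list opens as follows: "Health status variables include: chronic conditions; functional status, measured using the instrumental activities of daily living scale"; its other two entries are the participant's own ratings of health and of quality of life. The third group begins "Psychosocial status variables include: religion and religiosity, measured using the Duke University Religion Index" and goes on to two kinds of social support and a depression screen (PHQ-2). The section adds items on family experience of end-of-life decisions. Of the whole set it states: "They will also be used as covariates in the models testing the study hypotheses".

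**Analysis** is less definite. It plans "examination of potential covariates to reduce the expected within-groups dependency resulting from cluster randomization", and gives no rule for turning that examination into a model. **Primary Outcome** likewise refers to covariates that may matter without naming them.

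The estimator in **Primary Outcome** is GEE, described as "providing consistent estimates of regression coefficients and robust variance estimates". No small-sample correction, reference distribution or degrees of freedom is given. The section mentions both repeated measures and clustering of sites, but does not say which unit the robust variance is clustered on.

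**Power and Sample Size** sets the scale: "Based on an enrollment of 16 sites for the study (8 matched pairs"), 50 analysed per site, 5% against 15% at Month 6, and a one-tailed alpha of .05.

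**The concern.** A robust (sandwich) variance is estimated from between-cluster variation. With 16 clusters the uncorrected version is biased downward, and comparing the statistic with a normal distribution makes this worse. Each covariate fitted uses up more of the residual variation, so a long list should deepen the bias, particularly with few events.

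At stake is the false-positive rate of the primary test, which is already one-sided at 5%. The three sections also do not identify one model, so the covariates in the primary analysis could be settled after the data are seen.

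**Working it through.** **Plan's own figure.** Arcsine effect size h = 2·asin√.15 − 2·asin√.05 = 0.344. Without clustering, n per arm = 2[(1.645 + 0.842)/0.344]² ≈ 104.3. Multiplying by the design effect 1 + 49·ICC and setting the result to 400 gives ICC ≈ .058 (about .050 with t on 14 df). The plan states no ICC, so 800 can be neither confirmed nor refuted. The inflation 800/0.8 = 1000 reproduces.

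**Covariate count.** Sociodemographic 5 + health 4 + religion and religiosity 2 + two kinds of support 2 + depression 1 + family experience 1 = 15. Merging the religion pair and the support pair gives 13. Adding arm and intercept gives 17 or 15 parameters, before category coding or time terms.

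**Events.** No effect: 800 × .05 = 40. Planned effect: 400 × .05 + 400 × .15 = 80. With 17 parameters that is 40/17 = 2.4 to 80/17 = 4.7 events per parameter.

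**False-positive rate.** Two sets of simulated trials were run, with 3,000 trials per setting: 16 sites of 50, 5% in both arms, and a Month 6 logistic GEE with independence working correlation and variance clustered on site. The assumptions not in the documents are ICC .01 to .05, covariate ICC .05, covariates unrelated to outcome, and equal site sizes. Monte Carlo error is about .5 points.

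Set A, at ICC .03 / .05:

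| Covariates | Robust SE ÷ true SD | Uncorrected, one-sided z | Mancl-DeRouen SE, t(14) |
|---|---|---|---|
| 0 | 0.88 / 0.83 | 7.7 / 9.2% | 4.4 / 5.4% |
| 5 | 0.87 / 0.82 | 8.1 / 9.2% | 4.2 / 5.5% |
| 15 | 0.83 / 0.79 | 9.2 / 11.0% | 3.9 / 4.9% |
| 22 | 0.80 / 0.77 | 9.9 / 11.3% | 4.3 / 5.0% |

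Over ICC .01 to .05, set A gave 7.0–9.2% with no covariates and 7.6–11.0% with 15. The SE ratios were 0.83–0.90 and 0.79–0.87. With 15 covariates the corrected test gave 2.8–4.9%.

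Set B, uncorrected, at ICC .01 / .03 / .05:

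| Covariates (parameters) | One-sided error |
|---|---|
| 0 (2) | 7.1 / 6.6 / 8.2% |
| 3 (5) | 7.6 / 7.6 / 8.4% |
| 13 (15) | 8.4 / 8.6 / 9.7% |
| 15 (17) | 8.1 / 9.6 / 10.6% |

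**Share due to covariates.** Going from 0 to 15 covariates adds 9.2 − 7.7 = 1.5 and 11.0 − 9.2 = 1.8 points in set A, and 1.0, 3.0 and 2.4 points in set B. A further run put it at 0 to 2 points. In four of these five tabulated settings, more than half of the excess over 5% is already there with no covariates. For example, at ICC .05 in set A it is 4.2 of 6.0 points.

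**Other results.**
- A two-stage t test on site mean residuals held 4–6% with 15 or 24 covariates.
- Clustering on person instead of site gave 9–19%.
- Under 5% v 15% the true odds ratio is (.15/.85)/(.05/.95) = 3.35. The median estimate was 3.4 with no covariates and 3.5–3.7 with 15 to 24.

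**The case against.** **A reader might infer that having more parameters than sites makes the variance matrix singular, and that this is why the standard error is too small.** The results do not support that. With 17 parameters the site-clustered matrix does have rank at most 15, but the arm's own standard error can still be computed. The error rate rises gradually, with no break between 15 and 17 parameters, and it is already 7 to 9% with none.

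**The plan does not settle on all 15 variables.** This stands. The two analysis sections imply some selection, and 13 is a fair count. Selection without a rule is no cure, however: choosing covariates from the data still gave 8.4–9.4%.

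**Site clustering with a normal reference is a reading, not a statement.** This also stands. The plan does not exclude a correction, and it places GEE within a wider random-effects framework. But site is the natural unit in a cluster-randomized design, and clustering on person did worse at the higher ICCs.

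**The simulated covariates are unrelated to outcome, so any gain from adjustment is missing.** This is correct, and it is a reason to keep a few prognostic covariates rather than none.

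**A reader might also infer a large loss of participants with incomplete covariates.** If each of 15 items were independently missing in 1 to 3%, a complete-case model would lose 14 to 37%. But the plan does not specify complete-case analysis and gives no missing-item rates, and the baseline assessment is a face-to-face interview entered directly into a laptop. Only the absence of a rule for missing covariates can be noted.

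**Conclusion.** The point holds in a conditional form. If the robust variance is clustered on site, left uncorrected and referred to the normal distribution, the arm's standard error is about 10–17% too small with no covariates and 13–21% too small with 15. The nominal 5% test then runs at about 7 to 11%. The small number of clusters is the main cause. The covariate list contributes about 0 to 3 points, partly within simulation error, and a slight upward shift in the odds ratio.

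Shortening the list alone would not repair the test: three covariates without a correction still gave 7.6–8.4%. Correcting the test repairs the error rate even with all 15 retained, but leaves the model undefined, so both changes are worth making.

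These sizes rest on the assumed ICC range and on 16 equal sites. Participants and Recruitment also mentions matched senior living communities, so the number of sites may differ; 16 is the figure in the power section.

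**What to change.** **Primary Outcome:** state that the primary test treats site as the cluster, and choose one of two methods:
- GEE with a bias-corrected robust standard error (for example Mancl-DeRouen) and a t reference with site-based degrees of freedom (16 − 2 = 14); or
- a two-stage analysis that regresses the outcome on covariates without arm, then compares site mean residuals by a t test on sites, or on the 8 matched pairs (7 df).

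**Independent Variables:** replace the blanket sentence with a short, named list of prognostic covariates and keep the rest as descriptive. The number of ACP behaviors completed at baseline is an obvious candidate. Secondary Outcomes uses it for subgroups, yet it is not among the listed independent variables. Fill missing values of listed covariates by simple imputation or a missing category.

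**Analysis:** describe baseline differences, and do not choose covariates from baseline tests or from observed site dependency.

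**Cost:** wording only, plus somewhat less individual-level adjustment. Power for 5% v 15% with 15 covariates was .96, .84 and .72 at ICC .01, .03 and .05 with the corrected test, against .99, .93 and .85 uncorrected. The uncorrected values come from a test running above its nominal level, so they are not a fair benchmark. With no covariates the corrected values were .97, .86 and .74. If the sponsor expects an ICC near .05, the sample size should be rechecked against the corrected test.

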### **Description of Intervention Group**

Participants enrolled at the intervention site will receive four contacts, at baseline, two, four and six months. Each of the first three contacts consists of an integrated assessment and intervention feedback report, using an expert system. This is a software system consisting of an assessment battery, normative data on which to base decision rules, and materials that can be assembled for feedback. The assessment battery includes the core TTM measures, including Stages of Change (how ready the participant is to engage), Decisional Balance (DB) (attitudes regarding the pros and cons of engagement), and Values/Beliefs (V/B) (medical and religious beliefs that can affect readiness to engage in ACP). Participants are assessed for four different behaviors that together represent complete ACP engagement: communication with loved ones about views on quality of life versus quantity of life, communication with clinicians about views on quality of life versus quantity of life, assignment of a health care surrogate, and completion of a living will. The system takes the results of the assessment and results in an individualized feedback report. For individuals in early stages of change for a given behavior, the feedback focuses on changing attitudes, a necessary prerequisite for changing behavior, by addressing common barriers and by reminding individuals they can engage in small steps. For individuals in later stages of change, the feedback provides specific actions they can perform. In addition, if the participant has engaged in one ACP behavior but not another, the feedback provides information on how they can utilize what they have already accomplished in order to help them participate in any remaining ACP activities. Participants with a low pros score receive feedback suggesting additional pros they may not have realized, while participants with a high cons score receive feedback providing general strategies for overcoming the most common barriers to ACP. Participants also receive specific feedback for up to three items they endorsed on the V/B scale. A general introduction provides a common opening for the feedback report, briefly describing ACP, why it is necessary, and why individuals should engage in ACP even when it seems too difficult to plan for declines in health and dying. Whereas the baseline feedback report provides individualized normative feedback, the follow-up reports also provide ipsative feedback, in which the participants' current responses are compared to prior responses and feedback is provided on progress over time.

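### The named covariates omit the number of ACP behaviours already completed at baseline (0 to 3); putting it in the primary month-6 model is a cheap, modest gain in precision

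*Combined protocol and SAP*

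**What the plan says.** Independent Variables lists age, gender, ethnicity, education, income, several health measures, several psychosocial measures and items on family experience of end-of-life decisions. It summarises them by construct: "The independent variables will measure the constructs of sociodemographic status, health status, and psychosocial status". It gives them a role in the tests: "They will also be used as covariates in the models testing the study hypotheses". Neither baseline stage of change nor the number of behaviours already completed is on the list.

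Other sections bear on the point:

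- **Participants and Recruitment** excludes only people who have completed all four behaviours, so entrants have completed 0, 1, 2 or 3. Sites are matched on size, share of older patients and share of minority patients, not on prior ACP.
- **Description of Intervention Group** and **Description of Control Group** have stage of change assessed at baseline on the same scales in both arms. The intervention feedback provides for partial completers: "if the participant has engaged in one ACP behavior but not another".
- **Analysis** schedules "examination of potential covariates to reduce the expected within-groups dependency resulting from cluster randomization" among the baseline analyses. **Primary Outcome** describes models "incorporating both time and site level effects in addition to potentially important covariates". Neither names a covariate or gives a selection rule.
- **Secondary Outcomes** uses the baseline count, but only to define subgroups.
- **Primary Outcome** states the main hypothesis as "intervention group > control group at the final 6-month assessment". **Power and Sample Size** sizes the trial to "detect an absolute increase of 10% for ACP for the treatment group over the control group at Month 6".

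**The concern.** The primary outcome is action or maintenance on all four behaviours. A participant who enters with three done needs one more; a participant with none needs four. Few baseline variables could be more directly linked to the endpoint, yet this one is absent from the named covariates.

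Nothing else in the plan takes its place. The baseline occasion of the repeated-measures model cannot, since the composite, "because of our exclusion criteria, will be 0% at baseline", has the same value for everyone. The 2- and 4-month occasions come after the intervention has begun, so they are not baseline adjustment. The matching factors do not include prior ACP.

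With eight sites per arm, the mean count will differ between arms by chance, and the listed covariates are likely to remove only part of that difference. What is at stake is some precision and protection against this imbalance. The point concerns only the primary month-6 comparison.

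**Working it through.** **1. The plan's own figures.** From Power and Sample Size: 16 sites × 50 = 800 analysed; 800 / (1 − 0.20) = 1000 enrolled. Both reproduce. No intracluster correlation (ICC) is given, so it is inferred:

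- Arcsine effect: h = 2·asin(√0.15) − 2·asin(√0.05) = 0.344.
- Without clustering, one-tailed 0.05, power 0.80: n per arm = 2·(2.486 / 0.344)² = 104.3.
- Design effect implied by 400 per arm: 400 / 104.3 = 3.84, so ICC = (3.84 − 1) / 49 = 0.058. With a t reference on 14 df it is 0.050.

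**2. Assumptions, because the documents give no figures.** Counts 0/1/2/3 in 35/30/20/15% of participants; odds ratio 2 to 4 per behaviour already done; site ICC of baseline status 0, 0.05 or 0.10. With 5% overall in the control arm, the risks at counts 0 to 3 are:

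- odds ratio 2: 1.8, 3.6, 6.9 and 12.8%
- odds ratio 4: from 0.4% to 21%, a steep gradient

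**3. Why the gain depends on variation between sites.** The variance of the arm difference is proportional to ICC·(1 − R²between) + (1 − ICC)·(1 − R²within)/50. At ICC 0.058 the two parts are 0.058 and 0.942/50 = 0.0188, total 0.0768. At odds ratio 2 the count's R² is about 6.2%.

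- If it explains only within-site variance, the cut is 0.0188 × 0.062 / 0.0768 = 1.5%, and power goes from 0.763 to 0.769.
- If it explains between-site variance equally, the cut is 6.2%, and power goes from 0.763 to 0.786.

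**4. Simulation beyond the listed covariates.** 16 sites of 50 in 8 pairs, randomised within pair. The list was entered as 15 covariates with joint R² 0.25 for baseline status and a combined odds ratio of 1.3 per SD for outcome. Residual site variance was set so that the unadjusted comparison has about 0.80 power. Analysis: logistic GEE at month 6, independence working correlation, standardised risk difference, Mancl-DeRouen standard error, t on 14 df, 3,000 replicates in each of 22 settings (66,000 trials). Monte Carlo error of a variance ratio is about 0.01.

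Variance ratio (list + count over list) and power (list → list + count), 5% vs 15%:

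| Odds ratio | Site ICC 0 | Site ICC 0.05 | Site ICC 0.10 |
|---|---|---|---|
| 2 | 0.995; 0.823→0.826 | 0.977; 0.821→0.832 | 0.952; 0.830→0.840 |
| 3 | 0.976; 0.816→0.816 | 0.943; 0.819→0.840 | 0.923; 0.820→0.848 |
| 4 | 0.977; 0.811→0.818 | 0.935; 0.828→0.846 | 0.842; 0.836→0.884 |

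- No treatment effect: variance cuts of 1–2%, 2–6% and 4–11% across the three ICCs.
- Count unrelated to outcome (odds ratio 1, ICC 0.05): ratio 1.001, power 0.815→0.811, so no gain.
- Half the site variance in baseline status shared within pairs (odds ratio 4, ICC 0.10): ratio 0.917, a cut of 8%.
- Type I error: 0.032–0.040 with the count, 0.031–0.040 without.

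**5. Chance imbalance.** The count has mean 0.30 + 0.40 + 0.45 = 1.15 and variance 2.45 − 1.15² = 1.1275, so SD 1.06. With no site variation, the SD of the difference in arm means is 1.06·√(2/400) = 0.075; with site variation it reached 0.17 in simulation. An imbalance of 1 SD moves the list-adjusted risk difference by 0.4–1.3 percentage points at 5% vs 15%, and by 0.2–0.8 with no effect, against a planned 10. With no adjustment at all the shifts are 0.5–2.0 and 0.3–1.1.

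**The case against.** The strongest reply is that the plan already leaves room. It does not say that only the listed variables will be used; it schedules a look at potential covariates, allows further ones in the primary model, and shows through its subgroup plan that the authors have the count in mind. That stands: the count is not excluded, and the gap is one of commitment. Nor does leaving the choice open do much damage to the test. Taking the better of the models with and without the count gave type I error of 0.041–0.051, against 0.034–0.043 for either model fixed in the same check, so that is no part of the case.

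The second reply is that the gain is small. At odds ratio 2 it is about 1 power point or less, and the ratio of 0.995 lies within Monte Carlo error. The largest figures need a steep gradient, strong site variation and no help from matching, all at once. A list that predicts baseline status better leaves less to gain: in a further simulation at site ICC 0.05, with one score standing for the list, raising R² from 0.25 to 0.50 reduced the variance cut from 3.1% to 1.7% (odds ratio 2) and from 8.5% to 5.2% (odds ratio 3). The gain shrank but did not vanish.

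Two limits also stand. The simulation analyses month 6 alone, so the gain in the four-occasion GEE has not been computed. And the list may need more than 15 terms, against about 80 expected events (400 × 0.05 + 400 × 0.15), or 40 with no effect; convergence in simulation is then weaker reassurance. That concerns the length of the list more than the single term proposed here.

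**Conclusion.** The point holds, as a modest improvement and not as an error that invalidates the analysis. The named covariates leave out a baseline variable that is structurally tied to the endpoint and already collected in both arms, and no other feature of the design stands in for it. Under the stated assumptions, adding it to the list cuts the variance of the month-6 risk difference by 0.5–2%, 2–7% or 5–16% as the site ICC of baseline status goes from 0 to 0.05 to 0.10, with power gains of 0–1, 1–2 and 1–5 points. The gain is nil if the count does not predict outcome. It also guards against a chance imbalance that could move the estimate by up to about 1 point in 10. The count distribution, its odds ratio, its variation between sites and the strength of the listed covariates are all assumptions, so confidence in the exact size is medium.

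**What to change.** Pre-specify the number of ACP behaviours in action or maintenance at baseline (0 to 3, one linear term) as a covariate in the primary month-6 model, alongside the covariates already listed. Report the treatment effect as a standardised (marginal) risk difference, averaged over all participants analysed, with a site-cluster-robust standard error.

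The risk difference is the scale on which the trial was sized. It also avoids a misreading: in the simulations, adding the count moved a conditional odds ratio from about 3.6–3.9 to 3.9–4.9 while the risk difference stayed at 0.10.

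The cost is two sentences in the analysis section, one model degree of freedom and a standardisation step. No new data are needed. Every one of the 66,000 simulated fits with 15 listed covariates plus the count converged.
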